## 2 Trial Objectives and Design

## 2.1 Trial Objectives

**Primary Objective -** To determine the 6-month sustained, biochemically validated abstinence rates in smokers using EC compared to smokers offered UC.

## **Secondary Objectives -**

- 1. Among those who have not achieved full abstinence, to compare the number reporting at least fifty percent smoking reduction at 24 weeks in the EC versus the UC arm.
- 2. To compare the number achieving 7-day point prevalence quit rates at 4-, 12- and 24-week follow-up in the EC versus the UC arm.
- 3. To document changes in risky smoking practices (e.g., sharing cigarettes, smoking discarded cigarettes) from baseline to 4-, 12- and 24-weeks in both EC and UC arm.
- 4. To determine the cost-effectiveness of the intervention
- 5. To document fidelity of intervention implementation; mechanisms of change; contextual influences and sustainability.

## 2.2 Trial Design

Multi-centre two-arm cluster randomised controlled trial with mixed-method embedded process evaluation and economic evaluation.

A 6-month internal pilot with the first 120 participants (8 centres) is included to monitor recruitment within the given timeframe. The following stop/go criteria are specified: 90% recruitment achieved = go. Amber: 60-90% recruitment achieved = present action plan to Trial Steering Committee (TSC) with strategies for overcoming identified recruitment barriers. TSC to manage this plan with involvement of the study funder, and formally assess recruitment again at 12 months. Red: <60% = Rescue plan considered by TSC and funder; joint decision on whether the study should continue.

## 2.3 Setting

The study will take place in 32 non-residential homeless centres across five areas of GB: Scotland (N=6), Wales (N=3)Southwest (N=3), East England (N=6), Southeast England (N=6) and London

(N=8). Centres will be eligible if they are not exclusively residential; primarily targeted at people experiencing homelessness; not already providing EC to clients; and within 2 hours travelling distance from area university. Centres will need to agree to be randomised to either arm.

## 3 Subject Selection

## 3.1 Number of Subjects and Subject Selection

480 participants will be recruited from 32 homeless centres across Great Britain (15 participants per centre). Participants will be told about the study by centre keyworkers and, if interested, an appointment will be made to see a researcher to sign up for the study. Participants must be known smokers and known to the centre.

## 3.2 Inclusion Criteria

- Participants aged 18+
- Self-reported daily smoking as verified by staff working at the homeless centres
- Known to the homeless centre staff
- Willing and able to provide written consent (a translator can be provided)

## 3.3 Exclusion Criteria

- Pregnant or breastfeeding (to be reviewed upon new evidence)
- · Never or former-smoker
- · Currently using a smoking cessation aid
- · Unable or unwilling to provide written consent
- Allergic to any of the e-liquid ingredients (EC arm only)
- Not known to the centre staff

## allergic to any of the e-liquid ingredients (EC arm only) 4 Study Procedures

## 4.1 Informed Consent Procedures

At the baseline appointment participant consent will be obtained by the researcher to: a) take part in the study, b) be contacted regarding participation in qualitative process evaluation interviews, c) the sharing and appropriate linkage of anonymised data in accordance with the London South Bank University and European Social Research Council research ethics and government policies, and d). Individuals (participants and staff) who have indicated they are happy to be contacted to take part in an interview (process evaluation) will be followed up by local area RAs to confirm their participation. Those agreeing will provide further written consent prior to interviews and will consent to a) recording the interviews and b) the use of anonymised quotes in reports and publications.

## 4.2 Screening Procedures

Potential participants will be screened for eligibility by keyworkers before being invited to take part and further screening checks will take place during the baseline session.

## 4.3 Randomisation Procedures

Centres will be randomised (1:1 in permuted blocks), allocated to the EC intervention (n=16) or Usual Care (n=16) using permuted block randomisation to ensure balance. Where possible, staff at centres will obtain expressions of interest (EOI) from potential participants who meet the inclusion criteria before the centres receive training and are made aware of their allocated condition. Researchers will approach the first 15 who have expressed an interest in the study and invite them to a baseline session where informed consent will be taken. This approach is preferred over randomly selecting participants from the EOI list to reduce disharmony among clients attending centres. Our final sample size allows us to retain 90% if we under or over-recruit by +/- 3 in each centre (see section 6.3). The intervention the participant receives will be based on their centre's allocation. The trial statistician will create the randomisation list, which will be embedded/read in REDCap, which will be hosted by Kings College London (KCL).

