## **Control Group**

The control intervention will form usual care. Usual care (UC) here is defined as very brief advice (VBA) about smoking cessation and signposting to the local SSS with information about their local service. Although some homeless centres do offer more than this, this is not standard practice. In line with the current level of provision for smoking cessation in homeless centres, our control arm will include VBA to quit (in the form of an 'NHS choices' leaflet adapted for this population as used in our feasibility study) and signposting to the local SSS, including information about the location and opening hours of the service. Any centres with an established EC 'in house' provision or EC funding stream will be excluded (although this is uncommon). However, support or provision of EC from local SSS will be permitted as this constitutes part of UC. SSS vary widely in terms of services they offer; although all SSS offer NRT and behavioural support, only 11% of local authority funded SSS in England offer EC, whereas others who consider themselves 'e-cigarette friendly' offer support and advice around EC use.

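### As written, centre randomisation balances only the 16:16 count; stratifying by area would be a cheap improvement, because usual care and data collection are both organised locally

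*Protocol*

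**What the plan says.** Protocol section 4.3 states "Centres will be randomised (1:1 in permuted blocks"), with centres "allocated to the EC intervention (n=16) or Usual Care (n=16) using permuted block randomisation to ensure balance". It leaves the list to the trial statistician. Neither that section nor any other names a stratification factor, a minimisation rule, a block size or the order in which centres enter.

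Section 2.3 places the trial in "32 non-residential homeless centres across five areas of GB", then lists "Scotland (N=6), Wales (N=3)Southwest (N=3), East England (N=6), Southeast England (N=6) and London" (N=8). That is six areas, of 6, 3, 3, 6, 6 and 8 centres.

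Section 4.4, under Control Group, defines usual care as very brief advice plus "signposting to the local SSS with information about their local service". It adds that "SSS vary widely in terms of services they offer" and that "only 11% of local authority funded SSS in England offer EC"; e-cigarettes obtained that way count as usual care.

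Under section 7.3, research assistants in each area are responsible for completion of the case report forms and area leads sign them off. Under section 7.7.2, area leads check 10% of the entries.

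On imbalance, section 6.4 offers only adjustment for cluster-level and individual-level variables found to differ between arms at baseline. Area is not named.

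**The concern.** Permuted blocks without strata control one thing, the running count of centres per arm. They do nothing for area unless centres happen to enter grouped by area. Area is known before allocation and is linked, at least in part, to what usual care contains and to which staff gather the outcomes.

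With only 32 units to randomise, uneven splits by area are common. A visibly uneven allocation makes the result harder to interpret, gives up precision that stratification could have secured, and invites the criticism that the arms differed in local services or data-collection teams. It also touches research question 2 in section 1.3, on geographic context. Section 6.4.2 plans process-evaluation interviews in two Welsh centres, and if all Welsh centres were usual care there would be no e-cigarette delivery in Wales to study.

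This cannot be left to the statistical analysis plan. Section 6.4 has that plan finalised before data collection is complete, by which time centres will have been allocated.

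**Working it through.** **The plan's own figure.** The protocol gives no figure for area balance. Its sample size (section 6.3) reproduces and is not affected. For 6.25% against 0.5%, two-sided 0.05 and 90% power, the pooled formula without continuity correction gives 206 per arm. The design effect is 1 + (15 − 1) × 0.01 = 1.14, and 206 × 1.14 = 234.8, so 16 clusters of 15 = 240 per arm.

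**Inputs for area balance.** 32 centres, 16 per arm (section 4.3); areas of 6, 3, 3, 6, 6 and 8 (section 2.3). Block size and entry order are not stated, so both are assumptions and were varied.

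**Entry order unrelated to area.** The number of an area's centres in one arm is then hypergeometric.
- All three Welsh centres in one arm: 2 × C(16,3) / C(32,3) = 2 × 560 / 4960 = 22.6%. The same holds for Southwest. All three in usual care: 560 / 4960 = 11.3%.
- A 6-centre area split 5:1 or 6:0: 2 × [C(16,5) × 16 + C(16,6)] / C(32,6) = 2 × (69,888 + 8,008) / 906,192 = 17.2%.
- London split 6:2 or worse: 2 × [C(16,6) × C(16,2) + C(16,7) × 16 + C(16,8)] / C(32,8) = 2 × (960,960 + 183,040 + 12,870) / 10,518,300 = 22.0%.
- Jointly, by simulation, at least one area differing by 4 or more centres: about 52% with six areas, 58% with Wales and Southwest as one. With six areas, blocks of 2, 4 and 8 give the same answer.

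**Entry strictly area by area, in the listed order.**

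| Block size | Some area differs by 4 or more (six areas) | Some area wholly in one arm (six areas) |
|---|---|---|
| 2 | 0% | 0% |
| 4 | 0% | 17% |
| 8 | 12% | 33% |

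With Wales and Southwest as one area, blocks of 8 give about 20% in the first column.

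**Stratified by area, blocks of 2.** The 6- and 8-centre areas split 3:3 and 4:4 and the 3-centre areas 2:1, so no area differs by more than one centre.

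**Room for adjustment afterwards.** Expected quitters are 240 × 0.0625 = 15 and 240 × 0.005 = 1.2, about 16 in all. That is little information for five or six area terms, and an area lying wholly in one arm offers no within-area comparison.

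**Two details of the remedy.**
- If Wales and Southwest form one stratum of 6 split 3:3, there are C(6,3) = 20 equally likely splits, and 2 of them put all Welsh centres in one arm: 10%.
- If blocks of 2 and 4 are drawn freely within strata of 6, 6, 6, 6 and 8, some blocks are cut short and 16:16 is missed in about 42 to 43% of lists.

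**The case against.** The sentence in section 4.3 is not false. It gives 16 and 16 and says blocks are used for balance, and blocks deliver that count. The section is also silent on strata rather than excluding them. Both points stand: this is an improvement to the stated method, not an error in the text.

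A reader might infer that area imbalance confounds or biases the result. The documents do not support that. Chance imbalance leaves the randomised comparison unbiased in expectation, the primary model has random centre effects, and the sample size allows for an ICC of 0.01.

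Nor is there evidence of a large shift through usual care. Assume all usual-care quitting sits in one 6-centre area: its rate is 0.5% × 32/6 = 2.67%. With 5 of that area's centres in usual care, the arm's rate becomes 5/16 × 2.67% = 0.83%. That is a shift of 0.33 points against a planned difference of 5.75. This stands too, although it does not cover differences between area teams or areas in the e-cigarette arm, for which the documents give no figure.

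A reader might also take area to fix which service forms usual care. The protocol speaks of local and local-authority services, a finer level than Scotland or Southeast England. Area is a partial proxy, so stratifying by it would not fully balance service provision.

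Finally, section 6.4 does provide adjustment for imbalance. That fallback is weak: it depends on what is observed, does not name area, and has few events to work with.

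**Conclusion.** The point holds as a cheap improvement. As written, the randomisation guarantees 16:16 and nothing about area.

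The chance of a difference of 4 or more centres in some area is about 52% (58% with five areas) if entry order is unrelated to area. It falls to between 0% and 12% (20% with five areas) if centres enter area by area in blocks of 2 to 8. The 52% should therefore not be read as unconditional. The 23% chance that all Welsh centres share an arm likewise assumes that entry order is unrelated to area.

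What is at stake is the precision, credibility and interpretability of the one allocation that is realised, not validity in expectation. The consequence for the estimate cannot be sized from the document. The sample size is unaffected.

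**What to change.** 1. Settle section 2.3 first: it says five areas and lists six, and the strata depend on the answer.
2. State in section 4.3 that centres are randomised 1:1 in permuted blocks stratified by area, with concealed block sizes chosen to fill each stratum exactly. Pre-set concealed orderings of 2s and 4s would do this and keep 16:16; freely varying block sizes would not.
3. For the two 3-centre areas, either combine Wales and Southwest into one stratum of 6 and acknowledge the 10% chance that all Welsh centres share an arm, or keep them separate with 2:1 in one and 1:2 in the other. The second choice also gives 3 + 2 + 1 + 3 + 3 + 4 = 16 per arm.
4. Prespecify how area enters the primary analysis, in a form with few parameters, instead of leaving it to observed baseline differences.

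The cost is a different list from the trial statistician before the first centre is allocated. The drawback is that allocation becomes somewhat more predictable within an area. This matters because section 4.3 has expressions of interest collected before allocation is known only where possible; fixed blocks of 2 would make every second centre in an area predictable.

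If centres have already been allocated, stratification is no longer available. Report the allocation by area and prespecify how area is handled.

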## Staff training

Staff training needs have been identified from our scoping and PPI work and we have developed and tested a 2-hour education and training course in our feasibility study. Training will be provided for staff at each centre in both arms immediately prior to the recruitment period. The educational content follows National Centre for Smoking Cessation and Training (NCSCT) recommendations. This includes: information on smoking prevalence and patterns in the general population and in disadvantaged groups; health effects of smoking and benefits of cessation; evidence based smoking cessation treatment; misperceptions around smoking cessation in the context of other addictions and mental illness and study importance. Additionally, staff in the EC arm will be provided with information on the evidence base of EC use and effectiveness. Information about how to deliver correct advice about EC to participants will be provided along with a practical hands-on demonstration and practice around EC assembly, how to use the device, charge it, refill the tank, replace coils and battery safety is also provided. Staff in the UC arm will receive additional information about how to signpost clients to their local SSS.

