## 4.9 Schedule of Assessment

Table 1: Schedule of enrolment, interventions, and assessments.

	STUDY PERIOD					
	Enrolment	Allocation	Po	st-alloca	tion	Close-out
TIMEPOINT**	Baseline	0	4- week	12- week	24- week	t x
ENROLMENT:						
Eligibility screen	Χ					
Informed consent	Χ					
Allocation		Х				
INTERVENTIONS:						
Usual care		Х				
EC		Х				
ASSESSMENTS:						
Sociodemographic characteristics	Χ					
Mental health status	Х					
CO breath sample	X		Х	Х	Х	
Smoking behaviour (incl. risky smoking practices)	Х		Х	Х	Х	
Motivation to Stop Smoking (MTSS)	Х		Х	Χ	Х	
Fagerström Test of Cigarette Dependence (FTCD)	Х		Х	Х	Х	
7-day point prevalence & 50% smoking reduction			Х	Х	Х	
Thoughts about EC	Χ		Х	Х	Х	
Adverse effects	X		Х	Х	Х	
Use of EC & unintended consequences (EC arm)			Х	Χ	Х	
EC positive effects & EC support (EC arm)			Х	Х	X	
Smoking cessation support	X		Х	X	X	
received  Health-care service use	X		Х	X	X	
Health Related Quality of Life	X		Х	X	X	
Substance use	X					
AUDIT-C	X					
Assessment of main effectiveness outcome					Х	
Debrief					Х	Х

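### Listing interested clients before a centre learns its arm is only a preference, with no fallback, so the protocol permits recruitment by staff who know the allocation

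*Protocol*

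**What the plan says.** Section 4.3 makes the centre the unit of randomisation: "Centres will be randomised (1:1 in permuted blocks), allocated to the EC intervention (n=16) or Usual Care (n=16"). On the order of events it says: "Where possible, staff at centres will obtain expressions of interest (EOI) from potential participants who meet the inclusion criteria before the centres receive training". The same sentence ties training to the point at which centres learn their arm. No rule follows for a centre where this cannot be done. Researchers then approach the first 15 people who expressed interest and "invite them to a baseline session where informed consent will be taken".

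Centre staff do the earlier steps. Section 3.1 has keyworkers tell clients about the study, and section 4.2 adds: "Potential participants will be screened for eligibility by keyworkers before being invited to take part". The staff training part of section 4.4 says: "Training will be provided for staff at each centre in both arms immediately prior to the recruitment period". That training has arm-specific content.

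One exclusion in section 3.3 depends on the arm: "Allergic to any of the e-liquid ingredients (EC arm only").

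The schedule in section 4.9 ("Table 1: Schedule of enrolment, interventions, and assessments") puts consent and baseline measures in an enrolment column ahead of an allocation column. It does not show when staff, researchers or participants learn the centre's arm.

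**The concern.** When clusters are randomised, the arms stay comparable only if the people recruited do not depend on the allocation. Here one arm offers a free EC starter kit and four weeks of e-liquid. The other offers a leaflet and signposting. Staff who know which applies may mention the study to different clients, and clients who know may accept or decline for different reasons. EC centres could attract people ready to switch, or people who want the kit and have little intention to quit. The protocol does not allow the direction to be predicted.

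The first-15 rule stops staff choosing from a list, but it protects against selection only if the list was formed before disclosure. A client listed early can still decide on consent after the arm is known, and whoever replaces a decliner may be found by staff who know it.

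The planned analysis cannot be relied on to repair this. Counting losses as non-abstainers does not address who was recruited. Adjustment for variables that differ at baseline (section 6.4) covers measured factors only, and about 16 events support few covariates.

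**Working it through.** **Inputs from section 6.3.** 240 participants and 16 centres per arm, 15 per centre, ICC 0.01, two-sided alpha 0.05, quit rates 6.25% (EC) and 0.5% (UC), stated power 90%.

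**Reproducing the plan's figure.**
- Design effect: 1 + 14 × 0.01 = 1.14. Effective n per arm: 240 / 1.14 = 210.5.
- Power = Φ{[d − 1.96 √(2p̄(1 − p̄)/n)] / √([p1(1 − p1) + p2(1 − p2)]/n)}, with p̄ the mean of the two rates.
- Here d = 0.0575 and p̄ = 0.03375, so power = Φ[(0.0575 − 0.0345)/0.01738] = Φ(1.32) = 90.7%.

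The stated 90% is reproduced. The sample size is not in question.

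**How few events decide the result.** Expected quitters are 240 × 0.0625 = 15 and 240 × 0.005 = 1.2. One participant is 100/240 = 0.42 percentage points. With 1 UC quitter, 7 EC quitters give a Fisher p of 0.068 and 8 give 0.037 (clustering ignored).

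**Illustration.** Let f be the share of the EC arm recruited after disclosure, with the UC arm unaffected. Neither f nor the rate ratios come from the protocol; both are assumptions.
- *False significance, no true effect:* late EC recruits quit at 3 × 0.5%, so the EC rate is 0.005 × (1 − f + 3f).
- *Hidden benefit:* late EC recruits quit at half of 6.25%, so the EC rate is 0.0625 × (1 − f/2).

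Example for f = 50% with no true effect: EC rate 1.0%, p̄ = 0.0075, probability = Φ[(0.005 − 0.01648)/0.00841] = Φ(−1.37) = 8.6%.

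| f | EC rate, no true effect | P(significant for EC) | EC rate, benefit halved in late recruits | Power |
|---|---|---|---|---|
| 0 | 0.50% | 2.5% | 6.25% | 91% |
| 25% | 0.75% | 5% | 5.5% | 85% |
| 50% | 1.0% | 9% | 4.7% | 77% |
| 100% | 1.5% | 18% | 3.1% | 52% |

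**Dependence on the test.** With so few events the normal approximation is rough. I repeated the table with exact binomial probabilities at n = 210 per arm, for f = 0, 25%, 50% and 100%.
- Pooled z-test: P(significant for EC) is 0.8%, 2.6%, 5.8% and 15.1%; power is 96%, 91%, 83% and 54%.
- Fisher's test: P(significant for EC) is 0.03%, 0.2%, 0.7% and 4.0%; power is 92%, 85%, 73% and 37%.

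The direction is the same under each test, but the level is not. Neither test is the planned mixed-effects model.

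**The case against.** The protocol has real safeguards. Early expressions of interest are the preferred route, and the first 15 are approached rather than chosen. A researcher takes consent and further checks are made at baseline (sections 4.1 and 4.2). Eligibility does not depend on wanting to quit. Motivation and dependence are measured at baseline in both arms, the model adjusts for variables that differ, and screening and enrolment logs are kept (section 7.2). All of this stands and lowers the risk. It does not cover the centre where the list is formed after disclosure, and it does not settle what participants know at consent.

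Two stronger readings are tempting and not supported.

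- A reader might infer that section 4.3 places consent after disclosure and that Table 1 contradicts it. Section 4.3 orders only expressions of interest against training and disclosure. Consent after disclosure is a reasonable inference once section 4.4 puts training just before recruitment, but it is not stated. The table's allocation column may mean only the point at which a participant enters the centre's arm. The order is unclear, not contradictory.
- A reader might infer that selection could produce the planned effect by itself. At a 0.5% base rate that needs a 6.25/0.5 = 12.5-fold higher tendency to quit across the whole EC arm. Even a fourfold rise across the whole arm (0.5% to 2%), which gives about 28% by normal approximation and 11% by Fisher's test, presumes that the early list failed at every EC centre.

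It is also fair to say that a sensitivity analysis can sit in the SAP that section 6.4 promises. The order of recruitment cannot, because it is trial conduct and is lost once it has happened.

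**Conclusion.** The point holds as a gap in the recruitment procedure. The main safeguard against selection is conditional and has no fallback, the staff who learn the arm also identify and screen clients, and awareness of the arm at consent is left open. The realistic risk is an inflated or diluted estimate, or a false significant result, because a handful of participants can decide the comparison.

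The size rests on assumed shares and rate ratios. If late recruitment is rare the effect is small: at 25% late, the normal approximation gives about 5% in place of a nominal 2.5%, or 85% power in place of 91%. If late recruitment is general the effect is serious. Under Fisher's test the chance of false significance stays below the nominal 2.5% unless most of the arm is recruited late, while the loss of power is as large or larger. The document gives no ground for predicting which direction would occur.

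**What to change.** In section 4.3:

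1. Make it the rule that REDCap releases a centre's arm, and arm-specific training is given, only after the centre's ordered list of expressions of interest (15 plus reserves) is locked.
2. Take consent and baseline measures before the participant is told the arm, and mark the point of disclosure in Table 1.
3. State a fallback for centres that cannot fill the list. Record for each participant whether the expression of interest preceded disclosure, and report these numbers by arm and centre.
4. Prespecify, in the protocol or the SAP, a sensitivity analysis restricted to participants whose expression of interest preceded disclosure.
5. Because one exclusion applies in the EC arm only, state how eligibility is assessed before disclosure so that exclusions do not differ by arm.

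**Cost.** The change needs protocol wording, resequencing of the arm-specific part of training, one extra recorded item and a little more analysis. The sample size of 480 is unchanged. Centres slow to fill their lists may start later, which may bear on the recruitment progression criteria (section 2.2 and Table 2 in section 7.7.2), so the list deadline should be set with those in view.

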## 6.3 Sample Size

Our sample size is based on our feasibility trial. For, 0.05 alpha (two-tailed), 90% power, and cluster size of 15 participants (the feasibility study average in day centres (5)), this trial requires 240 participants per arm and 16 clusters per arm (480 participants and 32 clusters in total) to detect a difference of 5.75 between arms (i.e. 6.25% vs 0.5% respectively in the EC vs UC arms). The intraclass correlation coefficient (ICC) was set at 0.01 assuming equal cluster sizes. A final sample of 480 provides 90% power if the cluster size was smaller (n = 12) or greater (n=18) than the planned 15 participants per cluster.

There is sufficient power to detect more modest differences with smaller cessation rates in the EC arm; for example, with 5% cessation rate in the EC arm (vs. 0.5% UC), allowing 81% power with an ICC of 0.01 and 74% with an ICC of 0.025.

Sensitivity sample size calculations were conducted for the secondary outcome measuring 50% CO reduction, as previous studies have shown that CO reduction is a good predictor of future successful smoking quit attempts (20). If we assumed a minimally clinical important difference (MCID) to be 10% (i.e. 13% EC vs. 3% NRT), for 90% power, ICC = 0.01, alpha = 0.05 (two-tailed) and cluster size 15, we would need 360 participants across 24 clusters in total.

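### Section 4.3 says 90% power survives a shortfall of 3 in each centre, but with the fixed 32 centres that means 384 participants and about 85% power

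*Protocol*

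**What the plan says.** Section 3.1 sets the recruitment plan: "480 participants will be recruited from 32 homeless centres across Great Britain (15 participants per centre". Section 4.3 allocates 16 centres to each arm and then says: "Our final sample size allows us to retain 90% if we under or over-recruit by +/- 3 in each centre (see section 6.3". The sentence leaves out the word power, but its reference to section 6.3 makes the meaning clear.

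Section 6.3 states the calculation: "For, 0.05 alpha (two-tailed), 90% power, and cluster size of 15 participants", leading to "this trial requires 240 participants per arm and 16 clusters per arm (480 participants and 32 clusters in total", for rates of "6.25% vs 0.5% respectively in the EC vs UC arms". It adds: "The intraclass correlation coefficient (ICC) was set at 0.01 assuming equal cluster sizes". Its statement about cluster size is: "A final sample of 480 provides 90% power if the cluster size was smaller (n = 12) or greater (n=18". The same section gives two more powers, for 5% vs 0.5%: 81% at an ICC of 0.01 and 74% at an ICC of 0.025.

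**The concern.** Both sections mention clusters of 12 and 18, but they hold different things constant. Section 6.3 fixes the total at 480 and lets the cluster size vary, so 12 per cluster means 480 / 12 = 40 clusters and 18 per cluster means 480 / 18 = 26.7 clusters. Section 4.3 keeps the 32 centres and lets recruitment in each go up or down by 3, so the total moves to 384 or 576. A power figure worked out for the first situation does not carry over to the second.

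The sentence describes the power of the primary comparison and errs in the favourable direction. Anyone using it to weigh a recruitment shortfall would take a 20% loss of participants (384 of 480) to cost nothing in power.

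**Working it through.** **Inputs, all from section 6.3 unless noted.** Two-sided alpha 0.05; 6.25% (EC) vs 0.5% (UC); ICC 0.01; equal cluster sizes; 16 clusters per arm (also section 4.3); 15 per cluster (also section 3.1). No inflation for dropout applies to the primary outcome, because section 4.6.1 counts participants lost to follow-up as non-abstainers.

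**Formulas.** For k clusters of size m per arm:

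- design effect DE = 1 + (m − 1) × ICC
- effective n per arm = k × m / DE
- unpooled z: power = Φ(d / √(V1/n) − 1.96), with d = p1 − p2 and V1 = p1(1 − p1) + p2(1 − p2)
- pooled z: power = Φ((d√n − 1.96√V0) / √V1), with V0 = 2p̄(1 − p̄) and p̄ the mean of p1 and p2

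For 6.25% vs 0.5%: d = 0.0575, V1 = 0.0625 × 0.9375 + 0.005 × 0.995 = 0.06357, p̄ = 0.03375, V0 = 0.06522.

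**Step 1: reproduce the protocol's own figures (32 clusters of 15).**

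- 6.25% vs 0.5%, ICC 0.01: DE = 1 + 14 × 0.01 = 1.14; n = 240 / 1.14 = 210.5; power 90.7% pooled, 91.1% unpooled. Stated: 90%.
- 5% vs 0.5%, ICC 0.01: same n; 80.8% pooled, 81.3% unpooled. Stated: 81%.
- 5% vs 0.5%, ICC 0.025: DE = 1.35; n = 177.8; 73.9% pooled, 74.5% unpooled. Stated: 74%.

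Both z versions reproduce all three stated powers. A continuity correction (85.3%) or an arcsine test (96.2%) does not reproduce the base 90%. A t version with 30 df gives 89.3% for the base case but 78.8% and 71.7% for the other two, so it is not used below.

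**Step 2: section 6.3 as worded (total held at 480).**

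- 40 clusters of 12: DE = 1.11; n = 240 / 1.11 = 216.2; 91.4% pooled.
- 26.7 clusters of 18: DE = 1.17; n = 240 / 1.17 = 205.1; 90.0% pooled.

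Section 6.3 is therefore right as written.

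**Step 3: section 4.3 as worded (32 centres fixed).**

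- 12 in each centre, total 384: n = 192 / 1.11 = 173.0 per arm. Standard error = √(0.06357 / 173.0) = 0.01917; 0.0575 / 0.01917 = 3.00; unpooled power = Φ(3.00 − 1.96) = 85.1%. Pooled: Φ(1.014) = 84.5%.
- 18 in each centre, total 576: n = 288 / 1.17 = 246.2; 94.4% pooled, 94.7% unpooled.
- 12 in each centre, 5% vs 0.5%, ICC 0.01: n = 173.0; 72.7% pooled, 73.4% unpooled, against 81% at 15 per centre.

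**Step 4: what 90% needs at 12 per centre.**

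- 19 centres per arm (38 centres, 456 participants): n = 228 / 1.11 = 205.4; 90.0% pooled, 90.5% unpooled.
- 18 centres per arm (36 centres, 432 participants): n = 216 / 1.11 = 194.6; 88.4% pooled, 88.9% unpooled.

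So 38 centres is the smallest equal allocation that reaches 90%.

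**The case against.** The best defence is that section 4.3 speaks of the final sample size and points to section 6.3, where that sample is 480. On that reading, some centres fall below 15, others exceed it, and the total holds. The arithmetic then supports the claim. With half the 32 centres at 12 and half at 18, the coefficient of variation of cluster size is 0.2, DE = 1 + ((1 + 0.04) × 15 − 1) × 0.01 = 1.146, effective n = 240 / 1.146 = 209.4, and power is 90.6% pooled (91.0% unpooled). This reading is possible and the fix should keep it. It is not the plain sense of a statement about under- or over-recruiting in each centre, and section 6.3 assumes equal cluster sizes. If it was meant, the sentence should say that the total stays at 480.

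It is also fair that the sentence is a side remark: no target, allocation, endpoint or analysis uses it.

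A reader might go further and infer that the trial steering committee and funder would let a 20% shortfall pass. The documents do not support that. Section 2.2 and Table 2 judge recruitment by percentage of target, and 384 / 480 = 80% falls in the amber band, which calls for an action plan and formal reassessment at 12 months. A reader might also infer that 90% at 12 per centre needs 40 centres, or that section 6.3 is miscalculated. Neither holds: 38 centres are enough, and 40 is only the number that keeps the total at 480.

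**Conclusion.** The under-recruitment half of the section 4.3 sentence is wrong as written. With 32 centres of 12 (384 participants), power is about 85% (84.5% pooled, 85.1% unpooled), roughly 5 points below the stated 90%. For 5% vs 0.5% it is about 73% rather than 81%. The over-recruitment half holds, at about 94%.

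The result rests on the protocol's own rates and ICC of 0.01, equal cluster sizes, and a design-effect z calculation, which the protocol does not name but which reproduces its three stated primary-outcome powers. The planned 480 participants in 32 centres of 15 do give the stated 90%, so this is a misstated power figure and leaves the sample size itself sound.

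**What to change.** Replace the sentence in section 4.3 with text such as: *Power stays at about 90% if centre sizes vary between 12 and 18 while the total remains 480; if all 32 centres recruit only 12 (N = 384), power is about 85%, and 90% at 12 per centre would need at least 38 centres (N = 456).*

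Section 6.3 needs at most a note that its 12 and 18 figures hold the total at 480, so that the number of clusters changes.

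The cost is a text correction and a less favourable stated figure. The 480 participants, 32 centres, 15 per centre and recruitment progression criteria all stay as they are.
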